## **List of Abbreviations and Definitions of Terms**

Abbreviation	Definition of Term
ADA	American Diabetes Association
AE	adverse event
AESI	adverse events of special interest
ALT	alanine aminotransferase
ANCOVA	analysis of covariance
ANOVA	analysis of variance
AST	aspartate aminotransferase
ATC	anatomical/therapeutic/chemical
BMI	body mass index
BUN	blood urea nitrogen
CBC	complete blood count
CRF	case report form
CVE	cardiovascular event
DSMB	data and safety monitoring board
ECG	electrocardiogram
FAS	full analysis set
FPG	fasting plasma glucose
HbA1c	glycosylated hemoglobin A1c
IWRS	interactive web response system
LOCF	last observation carried forward
MedDRA	Medical Dictionary for Regulatory Activities
NMP22	nuclear mitotic apparatus protein 22
OC	observed case

PT	preferred term
RBC	red blood cell
SAP	statistical analysis plan
SOC	system organ class
T2DM	type 2 diabetes mellitus
TEAE	treatment emergent adverse event
ULN	upper limit of normal
WBC	white blood cell
WHODRUG	World Health Organization Drug Dictionary

### 1 General Considerations

### 1.1 Purpose

The purpose of this Statistical Analysis Plan (SAP) is to describe the analyses that will be performed, to ensure that the data listings, summary tables and figures that will be produced and the statistical methodologies that will be used are complete and appropriate to reach valid conclusions regarding the study objectives. In particular, this SAP addresses analyses and reports to be provided using data from the following study:

Clinical Trial Protocol THR-1442-C-418: Efficacy and safety of EGT0001442 compared with placebo in subjects with type 2 diabetes mellitus inadequately controlled by diet and exercise and up to one oral anti-diabetes agent.

### 1.2 Responsibilities

The INC Research Data Management department maintains the clinical database for the trial. The INC Research Biostatistics and Statistical Programming departments will provide data summaries.

## 2 Study Objectives

## 2.1 Primary Objective

The primary objective of this study is to assess the efficacy of EGT0001442 in lowering HbA1c at week 24 compared with placebo.

## 2.2 Secondary Objectives

The secondary objectives of this study are:

- To assess the efficacy of EGT0001442 in lowering FPG at weeks 2 and 24 compared with placebo
- To assess the efficacy of EGT0001442 based on the proportion of subjects who reach the American Diabetes Association (ADA) target HbA1c of <7% in the EGT0001442 group compared with placebo
- To assess the effect of EGT0001442 on systolic and diastolic blood pressure compared with placebo
- To assess the effect of EGT0001442 on body weight compared with placebo
- To assess the change in HbA1c change over time, week 1 to week 96

• To assess the safety of EGT0001442 in patients with T2DM

## 3 Study Design

### 3.1 Brief Description

THR-1442-C-418 is a multinational, 2 arm parallel group, randomized, double-blind placebo-controlled study to compare treatment with once daily EGT0001442, 20 mg capsules to matching placebo in either treatment-naïve type 2 diabetic subjects (i.e. those not taking an anti-hyperglycemic agent for ≥16 weeks prior to study entry) or subjects treated with one oral anti-diabetes drug. The study design consists of a screening period, a 2-week placebo run-in (washout) period, and a 96-week double-blind treatment period. The primary analysis will take place after 24 weeks of double-blind treatment.

In the proposed study, diabetic subjects will be screened within 3 weeks of washout start. At screening visit, subjects who meet all the inclusion criteria, none of the exclusion criteria, and who consent to participate in the study will receive counseling for appropriate diet and exercise. Those who are on an oral anti-diabetic medication will discontinue the medication and receive placebo in this run-in period for  $14 \pm 3$  days. Eligible diabetic subjects who are treatment naïve and who control their hyperglycemia through diet and exercise will also receive placebo and the hyperglycemia will be monitored to ensure that their fasting blood glucose levels remain below 250 mg/dL during this interval of  $14 \pm 3$  days.

After the run-in period, approximately 300 subjects will complete the baseline assessment on day 1, after overnight fasting to confirm their eligibility. The subjects that remain eligible will be randomly assigned in a 1:1 ratio to receive either once daily EGT0001442 in 20 mg capsules or matching placebo, using a computer-generated allocation schedule. Randomization will be stratified by study center and screening HbA1c ( $\geq$ 7 to <8.5% or  $\geq$ 8.5 to  $\leq$ 10%). Each subject will be provided with study drug for 24 weeks, dosing instructions, diet and exercise counseling, and a glycemic control card for recording food and fasting glucose information on the days prior to each clinic visit

Each subject will be instructed to return to the clinic on weeks 2, 6, 12, 18, and 24 for safety monitoring and efficacy assessment including review of adverse events, concomitant medication, vital signs, ECG, physical examination, testing of blood chemistry and hematology laboratory parameters, and a urinalysis.

Subjects who complete the 24-week treatment period will continue receiving the study drug for an additional 72 weeks. Subjects who receive rescue medication due to poor glycemic control will continue to receive approved anti-diabetic medications and standard of care per investigator

Final – 22November2011 CONFIDENTIAL Page 8 of 30

decision, according to current treatment guidelines, during the 72 week follow-on period. In the weeks 25 to 96 treatment period, subjects must return to the clinic on weeks 36, 48, 60, 72, 84, and 96 for continuous safety monitoring and efficacy assessment, including review of HbA1c values, adverse events, concomitant medication, ECG, vital signs, and physical examinations. A follow up exit visit will be conducted one week after the last dose.

The overall study duration from screening until follow-up could last a maximum of 102 weeks for study subjects.

An independent Data and Safety Monitoring Board (DSMB) will monitor overall safety information during the EGT0001442 development program including this study. The safety review activity and potential risk benefit assessments utilized by the DSMB are documented in DSMB charter and a separate DSMB statistical analysis plan.

An independent cardiovascular adjudication committee is established to review cardiovascular events (CVE) occurring during the study, in a blinded fashion. These events include cardiovascular mortality, myocardial infarction, stroke, and hospitalization for acute coronary syndromes, urgent revascularization procedures, and other possible serious cardiovascular events. The adjudicated events will be documented and archived to allow a meta-analysis to be performed to assess if there is any increase in cardiovascular risk to an unacceptable extent at the time of completion of all phase 2 and 3 clinical studies. The evaluation and analysis of adjudicated cardiovascular events will be documented in a separate CVE statistical analysis plan.

This reporting and analysis plan for protocol THR-1442-C-418 will examine several efficacy and safety endpoints at planned analyses time points (described in Section 3.6). Two independent statistical teams from INC Research will analyze data from this study. One team will perform all planned blinded analyses during study conduct, as well as the final end-of-study unblinded analysis (i.e., after all subjects have completed 96 weeks and final follow-up, and the database has been locked.) The second team will perform planned unblinded analyses during the study conduct for continuous safety assessment by the DSMB and interim Week 24 analysis.

### 3.2 Subject Selection

The study population will include approximately 300 subjects diagnosed with T2DM that are inadequately controlled by diet and exercise or by treatment with a single oral anti-diabetes agent and who have an HbA1c level between 7% and 10%. The study will recruit subjects from approximately 35 trial centers in 4 countries.

### 3.3 Assessment Schedule

The study activities at each clinic visit are presented in the following table.

Final – 22November2011 CONFIDENTIAL Page 9 of 30

**Table 1: Schedule of Events** 

		ening un-in		Treati	nent w	eeks 1	to 24			Treati	nent w	eeks 25	to 96		Follow Up 
Visit Number	1	2	3	4	5	6	7	8	9	10	11	12	13	14	15
Time to Randomization Visit (weeks) 	-5	-2	0	2	6	12	18	24	36	48	60	72	84	96	1 wk f/u
Informed Consent	X														
Screening for I/E criteria	X	X	X												
Medical History	X														
Diet & exercise counseling 		X				X		X		X		X			
Diary & glucometer record review			X	X	X	X	X	X	X	X	X	X	X	X	X
Discontinue anti-diabetic medication		X													
Randomization			X												
Physical exam 	X					X		X		X		X		X	X
Vital signs	X	X	X	X	X	X	X	X	X	X	X	X	X	X	X
ECG	X		X					X			X			X	X
Dispense study medication		X	X		X	X	X	X	X	X	X	X	X		
Blood draw for clinical lab test 	X		X	X	X	X	X	X	X	X	X	X	X	X	X
Urinalysis 	X		X	X	X	X	X	X	X	X	X	X	X	X	X
NMP22 testing 	X		X					X		X		X		X	
$AE^7$			X	X	X	X	X	X	X	X	X	X	X	X	X
Con Med		_	X	X	X	X	X	X	X	X	X	X	X	X	X

Screening period may last up to 21 days (V1 to V2), Run-in period is to be 14±3 days (V2 to V3), V3 to V8 window is ±3 days, all other visit windows are the nominal duration from randomization ± 6 days.

Glucose meter will be dispensed at visit 2. Training on using glucometer and recording hyper- or hypoglycemia will be conducted on visit 2.

- A complete physical examination will be performed by the investigator at screening and at the termination visit. An abbreviated physical examination will include body weight and general assessment of the skin, heart, lungs and abdomen. Abbreviated physical examinations will be performed by the investigator at all other time points, unless clinically indicated.
-  Blood sample for these lab tests at the designated visit are listed as following. Fasting state must be confirmed.
  - V1: CBC, electrolytes, BUN, creatinine, Lipids (TG, TC, HDL-C), ALT, AST, bilirubin (total and direct), PT, HbA1c, FPG, TSH, Hepatitis Screen (HBsAg, HBcAb, HCV), serum pregnancy for women of childbearing potential
  - V3: CBC, electrolytes, BUN, creatinine, Lipids (TG, TC, HDL-c), ALT, AST, bilirubin (total and direct), HbA1c, FPG
  - V4: CBC, electrolytes, BUN, creatinine, HbA1c, FPG
  - V5: CBC, electrolytes, BUN, creatinine, HbA1c, FPG
  - V6: CBC, electrolytes, BUN, creatinine, Lipids (TG, TC, HDL-c), ALT, AST, bilirubin (total and direct), HbA1c, FPG
  - V7: CBC, electrolytes, BUN, creatinine, HbA1c, FPG
  - V8-V15 and ET: CBC, electrolytes, BUN, creatinine, Lipids (TG, TC, HDL-c), ALT, AST, bilirubin (total and direct), HbA1c, FPG. PT only at V8, and V15 or ET.
-  Clean catch sample to be collected at each visit and sent to the central lab. Urine drug screen on screening (visit 1). On-site urine dipstick to be performed at all visits except V2.
- NMP22 testing will be performed at screening (V1), randomization (V3), and at weeks 24 (V8), 48 (V10), 72 (V12), and 96 (V14) or when clinically indicated. For subjects who do not have baseline NMP22 testing following Protocol Amendment 1 (11 April, 2011), NMP22 testing will be performed in the next visit or within 4 weeks after Amendment is approved, whichever comes first.
- Adverse events of special interest are specified to be:
  - Cardio- and cerebro- vascular events,
  - Genitourinary infections
  - Increase in creatinine from baseline by 0.5 mg/dL or more
  - Increase in ALT, AST or bilirubin to >3x ULN
- Visit to be conducted one week after last dose of study drug whether subject early terminates from study or completes V14.

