1.1 EGT0001442 for the treatment of type 2 diabetes mellitus

EGT0001442, a candidate oral antidiabetic agent, is a potent, highly specific inhibitor of the renal Na+/glucose transporter SGLT2. It is a benzylbenzene C-glycoside of the same

chemical structural class as dapagliflozin. EGT00001442 elicits a prominent and predictable glucosuria in laboratory animals and in healthy and diabetic subjects in clinical studies.

Several previous non-clinical and clinical studies were conducted with EGT0001474, a now-discontinued crystalline formulation of EGT0001442 and L-proline in 1:2 stoichiometry. The mass ratio of EGT0001474 to EGT0001442 is 1.5:1. In this protocol, all studies performed with EGT0001474 are described in terms of the EGT0001442 content. For example if a study used 50 mg of EGT0001474 it is described as 33 mg of EGT0001442 (delivered as proline cocrystal). EGT0001474 and EGT0001442 have similar solubility in water, similar dissolution rates when formulated as capsules, and show similar exposure in rat, monkey, and human studies.

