1.1.2 Summary of Clinical data with EGT0001442

Clinical studies have been conducted to evaluate safety, tolerability, pharmacokinetics (PK), pharmacodynamics (PD), metabolism, and efficacy of EGT0001442. No deaths or study drug related serious adverse events (AEs) have been reported in the clinical trials. EGT0001442 up to 100 mg for up to 14 days was safe and tolerated in healthy volunteers. In a phase 2, double-blind, placebo-controlled study, subjects with type 2 diabetes mellitus were treated with EGT0001442 in doses of 5 to 50 mg or a placebo for 28 days. The most frequently occurring AEs were headache (4% in the placebo and 11% in the treatment groups), pollakiuria (none in the placebo and 4% in the treatment groups), fatigue (7% in the placebo and 2% in the treated group), and nausea (4% in the placebo and 3% in the treated group). No hypoglycemia was reported. Genital and urinary tract infections were observed in some subjects in the EGT0001442 treated groups, including balanitis candida, urinary tract infection, bacterial vaginitis, vulvovaginal candidiasis, and vulvovaginal mycotic infection.

Urinary glucose excretion (UGE) was measured in healthy and diabetic subjects. EGT0001442 increased UGE in a dose-dependent and saturable manner. The plateau in UGE corresponded to dosages of EGT0001442 above 20 mg/day. EGT0001442 treatment in subjects with T2DM for 4 weeks was effective in reducing FPG by 24 to 41.6 mg/dL in the

groups dosed with 5 to 50 mg/day EGT0001442. Subjects receiving EGT0001442 also had a reduction in body weight, blood pressure, and postprandial glucose compared to the changes in the placebo group. Details of the safety and efficacy information are described in the Investigator's Brochure

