6.7 Clinical Laboratory Tests

6.7.1 Laboratory Parameters

Subjects will be in a seated or supine position during blood collection. Schedule of each laboratory test is outlined in Appendix 1. Clinical laboratory tests will include the following:

Table 1.List of Laboratory Tests

Hematology:	Serum Chemistry:	
- Hematocrit (Hct)	- Albumin (ALB)	
- Hemoglobin (Hgb)	- Alanine aminotransferase (ALT;	
- Platelet count	- Aspartate aminotransferase (AST;	

Confidential Page 27 of 61

- Red blood cell (RBC) count
- White blood cell (WBC) count with differential

Urinalysis:

- Appearance
- Bilirubin
- Color
- Glucose
- Ketones
- Microscopic examination of sediment
- Nitrite
- Occult blood
- pH
- Protein
- Specific gravity
- Urobilinogen

Hepatitis screening HBsAg, HBcAg, and HCV

Urine drug screen

Urine human chorionic gonadotropin (hCG) (only for females who are not diagnosed as postmenopausal)

- Blood urea nitrogen (BUN)
- Calcium (Ca)
- Carbon dioxide (CO₂)
- Chloride (Cl)
- Creatinine
- Glucose
- Phosphorus
- Potassium (K)
- Sodium (Na)
- Magnesium
- Total bilirubin
- Direct bilirubin
- Total cholesterol
- High density lipoprotein cholesterol (HDL-C)
- Low density lipoprotein cholesterol (LDL-C, calculated)
- ApoB
- Total protein
- Triglycerides
- Uric acid
- Fasting plasma glucose
- HbA1c

Coagulation:

- Prothrombin time (PT)

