6.7.2.2 Urinalysis

Clean-catch, midstream urine samples will be collected per schedule outlined in Section 7.

Dipstick urinalysis will be conducted. Microscopy will be conducted if the subject has a positive result on any of the dipstick tests that require microscopic follow-up to clarify their significance.

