### 3.4 Blinding, Randomization, and Bias

Eligible subjects who complete the  $14 \pm 3$  day run-in period and meet all study inclusion/exclusion requirements will be randomized in a 1:1 ratio to receive EGT0001442 20 mg/day or placebo according to a computer-generated randomization schedule. Subjects will be assigned to treatment groups in sequential order as they qualify for the study, using a centrally located and managed interactive web response system (IWRS). Randomization will be stratified by study center and screening HbA1c ( $\geq 7$  to < 8.5% or  $\geq 8.5$  to 10%). The study will be conducted at multiple investigative sites and will likely involve variable numbers of subjects at each site. Enrollment will be on a competitive basis but each site will be capped at 15% of the total randomized subjects (45 subjects).

The study drug will be blinded to the sponsor, investigators, study coordinators, pharmacists, study subjects, and the cardiovascular adjudication committee members. Upon randomization, each subject will receive a subject randomization number and drug kit(s) assigned to the subject. To maintain blinding of the treatment, the values of the HbA1c after dosing starts will remain blinded to all study personnel and subjects until all subjects have completed the 24 week treatment period. After all subjects have completed the 24 week treatment period, all previous and subsequent HbA1c values will be made available to the sponsor, investigators, study coordinators, pharmacists, and the study subjects for close monitoring of subjects' safety including assessment of providing rescue medication. Subjects' treatment assignment will continue to be held from all study personnel so the remainder of the study can be conducted in a blinded fashion.

If knowledge of the test substance is needed to manage the subject's condition, the investigator will contact the IWRS to obtain the treatment assignment. If unblinding occurs for any reason, the time and reason for unblinding will be recorded on the case report form (CRF) and the sponsor must be notified within 24 hours.

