#### **9.2** Labs

### 9.2.1 Hematology, Chemistry and Urinalysis

Laboratory parameters include the following tests: hematology, chemistry, and urinalysis. Established or generally acknowledged methods, normal ranges, and quality control procedures will be supplied by the local and central laboratory for the study records.

Hematology parameters used in summaries include hematocrit, hemoglobin, platelet count, red blood cell (RBC) count, and white blood cell (WBC) count with differential. Chemistry

Final – 22November2011 CONFIDENTIAL Page 27 of 30

parameters (including lipids) used in summaries include albumin, ALT, AST, blood urea nitrogen, calcium, bicarbonate, chloride, direct bilirubin, glucose, magnesium, phosphorus, potassium, sodium, total bilirubin, total protein, uric acid, total cholesterol, LDL cholesterol, HDL cholesterol, triglycerides, and ApoB. Urinalysis parameters used in summaries include appearance, bilirubin, color, glucose, ketones, microscopic examination of sediment, nitrites, occult blood, pH, protein, specific gravity, and urobilinogen.

All laboratory parameters will be summarized for each treatment group, at every assessed time point using descriptive statistics and graphical displays of the means and standard deviations over time. In addition, for hematology and chemistry laboratory parameters, changes from baseline in these quantitative tests will be summarized by treatment group and at every assessed post-baseline time point.

Shift tables will be developed by first classifying the subject laboratory results as low, normal, or high in comparison to the applicable laboratory reference range. The number and percentage of subjects with indicated shifts (low, normal, high) in their results from baseline to each post-baseline assessment will be presented for all hematology, chemistry and applicable urinalysis parameters. All laboratory data will be listed.

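### Post-dose urine glucose is not withheld from sites, although the drug acts by glucosuria and HbA1c and plasma drug levels are withheld; investigators may gain partial information on treatment arm.

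*SAP*

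**What the plan says.** **Collection.** SAP Table 1 (Schedule of Events), footnote 5, has a clean-catch sample sent to the central laboratory at each visit and adds: "On-site urine dipstick to be performed at all visits except V2". Protocol 6.7.2.2 also states: "Dipstick urinalysis will be conducted".

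**Glucose is on the panel.** Protocol 6.7.1, Table 1, lists glucose under urinalysis. SAP 9.2.1 repeats it: "Urinalysis parameters used in summaries include appearance, bilirubin, color, glucose, ketones".

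**Mechanism.** Protocol 1.1 says the compound "elicits a prominent and predictable glucosuria in laboratory animals and in healthy and diabetic subjects in clinical studies". Protocol 1.1.2 adds: "The plateau in UGE corresponded to dosages of EGT0001442 above 20 mg/day".

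**What is withheld.** SAP 3.4 says: "To maintain blinding of the treatment, the values of the HbA1c after dosing starts will remain blinded to all study personnel and subjects", and this lasts until everyone has finished Week 24. Protocol 5.5 has the same rule. Protocol 5.8 keeps plasma drug concentrations from the study team until the primary-analysis data are locked. Neither blinding section mentions urine glucose.

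**Who sees and judges.** Protocol 6.9.1 makes the investigator review every laboratory result and judge abnormal ones against the subject's own baseline. It exempts high serum or plasma glucose and high HbA1c from adverse event recording, but does not mention urine glucose. Protocol 3.1 leaves rescue in the main period to the investigator after review of self-monitored and fasting plasma glucose. Under SAP 7.1, the HbA1c at rescue is carried forward to Week 24.

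**The concern.** The plan treats post-dose HbA1c and plasma drug level as threats to the blind and withholds both. Urine glucose is the variable closest to the mechanism, yet it is left open. A site could compare readings before dosing (visits 1 and 3) with those after dosing (visits 4 to 8 in the main period) in the same subject.

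Four judgement-based items could be affected:

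- whether and when a subject is rescued before Week 24, which determines the HbA1c carried into the primary analysis;
- other efficacy values up to Week 24, because SAP 5.3.2 treats post-rescue efficacy measurements as missing;
- the investigator's causality rating of adverse events;
- evaluation of genitourinary events, which are of special interest for this drug class.

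**Working it through.** **1. The plan's own figure.** SAP 3.5 assumes a difference of 0.4, SD 1.0, two-sided α 0.05 and 90% power. By the normal approximation, n = 2 × (1.960 + 1.282)² × 1.0² / 0.4² = 131.3, so 132 per arm. The noncentral t gives 133 per arm (power 0.901), as the SAP states. The protocol's 131 gives 0.897. Nothing in this point depends on an error in the sample size. The standard error of the difference is 1.0 × √(2/133) = 0.123 at 133 per arm and 1.0 × √(2/150) = 0.115 at 150.

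**2. Exposure to the cue.** The dipstick is done at 14 of 15 scheduled visits: two before dosing (1 and 3), five in the main period after dosing (4 to 8), six in the extension (9 to 14) and the follow-up visit.

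**3. Markers of treatment set side by side.**

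| Marker | Visible to sites before Week 24? | Source |
|---|---|---|
| HbA1c | No | Protocol 5.5, SAP 3.4 |
| Plasma drug level | No | Protocol 5.8 |
| Fasting plasma and self-monitored glucose | Yes; stated basis for rescue | Protocol 3.1 |
| Urine glucose, central laboratory | Not withheld in any supplied text | SAP Table 1, 9.2.1 |
| Urine glucose, on-site strip | Not stated; pads not named | SAP Table 1, footnote 5 |

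**4. How much one reading could reveal.** The documents give no positivity rates. Assume P(positive | active) = s between 0.95 and 0.99, and P(positive | placebo) = p between 0.05 and 0.70. The placebo range is wide because subjects who stop an oral agent and enter with glucose up to 250 mg/dL may also spill glucose. At 1:1 allocation:

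- Correct guess = (s + 1 − p)/2. Best case (0.99 + 0.95)/2 = 0.97; worst case (0.95 + 0.30)/2 = 0.625; chance is 0.50.
- P(active | positive) = s/(s + p). Worst case 0.95/1.65 = 0.58; best case 0.99/1.04 = 0.95.
- P(placebo | negative) = (1 − p)/[(1 − p) + (1 − s)]. Worst case 0.30/0.35 = 0.86; best case 0.95/0.96 = 0.99.

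A negative reading is the more telling one. These figures are for one reading alone and do not net off what fasting glucose already shows.

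**5. What it could do to the primary difference.** Let f be the extra share of placebo subjects rescued early because of an inferred assignment. Let d be the HbA1c carried forward minus the value that would otherwise have been used at Week 24. The shift is f × d. Neither input is in the documents. Assume f of 0.05 to 0.15 and |d| of 0.3 to 0.6:

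- Smallest: 0.05 × 0.3 = 0.015, which is 4% of 0.4 (0.13 standard errors at 150 per arm).
- Largest: 0.15 × 0.6 = 0.09, which is 22.5% of 0.4 (0.78 standard errors).

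The sign of d sets the direction. At 133 per arm, by the noncentral t:

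- d positive (carried value too high): the comparison favours the drug. The two-sided rejection rate under no drug effect rises from 0.05 to 0.052 (shift 0.015) or 0.113 (shift 0.09).
- d negative (subjects would have worsened further): the difference shrinks to 0.385 or 0.31, and power falls from 0.901 to 0.879 or 0.712.
- d near zero: no shift. SAP 3.5 assumes no substantive mean placebo change; if the extra rescued subjects followed that average, this case would apply.

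**The case against.** **On-site glucose reading is inferred.** Footnote 5 names no pads. The only pads the documents name as triggers are white cells and blood (Protocol Appendix 1), so the strip may serve infection and haematuria screening alone. This stands for the strip. It does not dispose of the central-laboratory result, which includes glucose and falls under the investigator's review duty.

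**A reader might infer that sites can identify the arm.** The documents do not support that. Placebo subjects may also spill glucose, and no placebo rate is given. An entry limit of 250 mg/dL does not make a positive reading specific to active drug. Nor does any figure show that HbA1c would be a weaker cue than urine glucose.

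**Other cues remain.** Fasting plasma and self-monitored glucose stay visible by design and are the stated inputs to rescue. Masking urine glucose removes one cue of several, and its added information cannot be estimated from the documents. This stands, and it limits the benefit of the fix.

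**Some outcomes are better protected.** Cardiovascular events go to a blinded committee, and Protocol 6.9.7.1 asks for signs, symptoms and infectious agent for genitourinary infections. That lessens the concern for those events without removing judgement from initial reporting or causality.

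**The HbA1c analogy ends at Week 24.** Once all subjects have completed Week 24, HbA1c is released to sites to help decide on rescue. This stands. Masking urine glucose beyond that point rests on assignment itself remaining blinded to Week 96 (SAP 3.4).

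**Later protocol versions are not supplied.** The SAP cites versions of April, August and September 2011, and a masking rule there cannot be excluded. SAP 3.4, in the plan dated 22 November 2011, mentions none.

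**Conclusion.** The point holds as a gap in blinding procedure: no supplied text withholds post-dose urine glucose, although the drug's mechanism is glucosuria and two other treatment markers are withheld. The supportable conclusion is that investigators may gain partial, probabilistic information on arm beyond fasting and self-monitored glucose, and that this could influence rescue, causality ratings and genitourinary event evaluation.

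A reader might go further and infer that the trial is effectively unblinded, or that the primary result is biased in the drug's favour. Neither follows. The shift of 0.015 to 0.09 points is an illustration under assumed rescue shares and HbA1c differences. It could run in either direction or be nil, and its lower end is negligible. The effect on adverse event judgements cannot be sized. The case for acting is that the gap is specific and cheap to close, not that harm has been shown.

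**What to change.** - Extend the masking rule in Protocol 5.5 and SAP 3.4 to post-randomisation urine glucose. Withhold the central-laboratory value from sites and blinded sponsor staff while treatment assignment is blinded. It remains available for the SAP 9.2.1 summaries after unblinding.
- State which pads the on-site strip carries. Use strips without a glucose pad, or instruct sites not to read or record it. Keep the white-cell and blood triggers for microscopy and culture in Protocol Appendix 1.
- Add a matching exception to the laboratory-review duty in Protocol 6.9.1. Otherwise the masking rule would contradict it.
- If a later protocol version already contains such a rule, cite it in SAP 3.4.

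No change to any rescue rule is involved. The cost is a laboratory report setting, a strip choice or site instruction, and wording in three sections. Sites lose a urine glucose reading that no protocol decision uses. Fasting plasma and self-monitored glucose remain as partial cues.
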